### **5.3.3      *Sensitivity Analysis***

No sensitivity analyses are planned.

### **5.3.4      *Supplementary Analyses***

To explore the treatment effect while trial is ongoing, the ORR may be presented also for the RES.

Due to the low sample size, no subgroup analyses are planned.

## **5.4      Secondary Endpoint(s) Analysis**

### **5.4.1      *CBR and VGPR in RRMM***

The clinical benefit rate (CBR) will only be derived for the RRMM subjects, and is defined as a BOR of MR, PR, VGPR, CR or sCR.

Similarly, VGPR is defined for RRMM subjects with BOR of VGPR, CR or sCR.

CBR and VGPR will be reported with its exact 95% CI, calculated by the Clopper-Pearson method and will be presented together with the ORR.

### **5.4.2      *CRR***

The proportion of subjects in the analysis set with a complete response (CR) or better will be analyzed as the ORR, and may be presented together with the ORR.

### 5.4.3 DOR

Duration of response (DOR, months) is defined as time from date of first documented initial response (PR or better) to date of progression, or death, whatever comes first. As such, DOR is defined only for the subjects (in the analysis set) who achieve PR or better. DOR will be censored following the censoring scheme for time to event variables as presented in [Table 8](#).

**Table 8: Censoring scheme for time to event variables**

Situation	Date of Progression or Censoring	Censoring Rule
Incomplete or no baseline assessments	C1D1, or date of randomization	Censored
No documented PD or death prior to analysis data cutoff, trial discontinuation, start of new anti-cancer treatment	Date of last valid tumor assessment with no documented PD before the situation*	Censored
Documented PD between adequate** assessment visits	First date of assessment demonstrating documented PD	Event
Death before first response assessment	Date of death	Event
Death between adequate** assessment visits	Date of death	Event
Death or documented PD after two or more consecutive missed visits***	Date of last valid tumor assessment prior to the missed visits*	Censored

\*Excluding response assessments with NE as overall time point response. If no such assessment exists, the censoring date will be C1D1.

\*\* No more than one missed visit, no anti-cancer therapy etc. before the death or documented progression.

\*\*\* Please refer to the DPS for the definition of two missed scans.

Clinical progression (as recorded in eCRF) does not constitute documented progression and will cause censoring (unless documented progression was recorded before clinical progression).

DOR will be estimated using the KM method and the result will be displayed graphically. The number and percentage of subjects with event or censoring will be reported. Median DOR (months) with associated 95% CI as well as first and third quartiles and range will be provided.

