## **7 DISCONTINUATION OF TRIAL TREATMENT AND SUBJECT DISCONTINUATION/WITHDRAWAL**

### **7.1 Discontinuation of Trial Treatment**

A subject's trial drug must be discontinued if:

- Adverse event requiring treatment discontinuation according to stopping rules in Section 6.6.2 (for GEN3014) and Section 6.6.3 (for daratumumab SC)\*
- Subject non-compliance
- The subject initiates treatment with a prohibited medication
- The subject received concurrent (non-protocol) treatment for MM, AML, or DLBCL.
- Sponsor decision
- Subject request to discontinue trial treatment\*
- Pregnancy
- Clinical progression\*
- Disease progression (according to response criteria, Section 8.2)
- Other

\*Every effort should be made to continue evaluations according to the trial protocol. When a subject discontinues trial drug, the subject remains in the trial and is followed until meeting 1 of the reasons listed in Section 7.2.

If a subject's trial drug must be discontinued before the end of the treatment regimen, this will not result in automatic withdrawal of the subject from the trial. The End of Treatment assessments should be performed. In addition, the subject will still be followed for the safety follow-up visit (see Section 7.1.1) and for survival status (see Section 7.1.2) through the end of the trial.

Subjects should be examined regularly according to the Schedule of Activities (Section 1.3), or more frequently, as needed. If the decision to discontinue trial drug occurs around the time of the next planned treatment administration visit, the assessment schedule for the End of Treatment Visit should be followed. Subjects should be followed for safety as detailed in Section 7.1.1 and Section 10.3.

After treatment discontinuation, the subject should receive suitable treatment as decided by the investigator (see Section 6.8).

Trial treatment assigned to the withdrawn subject may not be assigned to another subject. Additional subjects will be entered to ensure the protocol-specified number of subjects complete the trial.

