#### **8.4.5 Disease-Related Events/Outcomes and Other Events/Procedures Not Qualifying as Adverse Events or Serious Adverse Events**

##### ***8.4.5.1 Disease Progression or Death***

Events that are clearly consistent with the expected pattern of progression of the underlying disease should not be reported as AEs or SAEs.

1. That is, the terms “disease progression,” “progression of disease,” or “malignant disease progression” and other similar terms should not be used to describe an AE or SAE. These data are captured as efficacy assessment data only.
  - In most cases, the expected pattern of progression will be based on the response criteria. In rare cases, the determination of clinical progression will be based on symptomatic deterioration. However, every effort should be made to document progression through use of objective criteria.
  - Clinical symptoms that cannot be determined as reasonably due to progression of the underlying malignancy or does not fit the expected pattern of progression for the disease under study should be reported as an AE or SAE.
2. Hospitalization due solely to progression of the underlying cancer should not be reported as an SAE. See Section 10.3.1, under the definition of SAE, for additional reasons when hospitalizations should not be reported as SAEs.

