#### **9.4.3.4 Progression-Free Survival**

PFS is defined as the time from the date of first dose, or date of randomization for subjects in the Expansion Part B, to the date of progression or death (due to any cause), whichever comes first. PFS will be censored similar to Table C1 in Appendix C in the FDA Guidance for Industry: Clinical Trial Endpoints for the Approval of Non-small Cell Lung Cancer Drugs and Biologics ([FDA Guidance, 2015](#)), with further details to be provided in the SAP.

The PFS distribution will be estimated using the Kaplan-Meier method, and the Kaplan-Meier curves, medians, and 95% CIs of the medians will be presented. The number of events may be small, and thereby limit use of the Kaplan Meier method to provide reliable information. In this case, descriptive statistics (eg, n, mean, standard deviation, median, minimum, and maximum) for PFS will be presented.

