**Table 5: Analysis visit windows for efficacy summary listings in R/R DLBCL**

Analysis period	Target day (visit window per protocol)	Analysis visit window	Label on output
Baseline	1 (pre-dose C1D1)	Last data point prior to dosing	Baseline
Scheduled on-treatment disease assessments Week 6,	42 ( $\pm 3$ )	1 to 63	Week 6
	84 ( $\pm 3$ )	64 to 105	Week 12

12, 18, and 24, then every 24 weeks thereafter	126 ( $\pm$ 3)	106 to 147	Week 18
	168 ( $\pm$ 3)	148 to 252	Week 24
	336 ( $\pm$ 3)	253 to 420	Week 48
	...	...	...
Unscheduled	-	-	Unscheduled <Day x>
End of treatment	-	-	End of treatment

Response assessments should be performed until confirmation of disease progression, start of new anti-cancer therapy, withdrawal of consent, or death, whichever comes first.

Details on how to slot subject data that systematically is performed off schedule is provided in the ADaM specification, but no data should be disregarded for efficacy evaluations due to this windowing.

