#### **5.4.5 PFS**

Progression-free survival (PFS, months) is defined as the time from C1D1, or randomization, to first documented PD or death due to any cause, whichever occurs earlier (see Table 8 for censoring rules). PFS will be derived for all subjects and analyzed using similar methods as DOR.

PFS event-free rate at a landmark time T is defined as the probability that a subject has not progressed and is alive at time T. (Subjects with an intermittent event prior to the landmark will not be a part of the analysis.) PFS event-free rates at 6, 9, and 12 months (or later times if available) will be presented along with 95% CI.

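### The SAP's clinical-progression sentence censors PFS and DOR even when documented PD follows, against the endpoint definitions and Table 8's own event rows

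*SAP*

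**What the plan says.** For DOR, SAP 5.4.3 states "DOR will be censored following the censoring scheme for time to event variables as presented in" Table 8. For PFS, SAP 5.4.5 runs the clock to "first documented PD or death due to any cause, whichever occurs earlier (see Table 8 for censoring rules". Both endpoints therefore take on everything attached to that table, including the sentence beneath it: "Clinical progression (as recorded in eCRF) does not constitute documented progression and will cause censoring (unless documented progression was recorded before clinical progression".

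The protocol's PFS definition (9.4.3.4) runs "to the date of progression or death (due to any cause), whichever comes first", and 9.4.3.2 defines the end of response in the same terms. Neither makes an exception for clinical progression. Section 9.4.3.4 leaves further censoring detail to the SAP.

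On conduct, Protocol 7.1 lists clinical progression as an asterisked reason for stopping drug. The asterisk says "Every effort should be made to continue evaluations according to the trial protocol" and keeps the subject in the trial. Protocol 8.4.5.1 allows that progression is, in rare cases, judged on symptoms, but adds that "every effort should be made to document progression through use of objective criteria". Protocol 7.1.2 has survival status checked every 3 months.

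**The concern.** A subject whose disease is judged clinically to have progressed is at higher short-term risk of documented PD or death than the subjects who remain under observation. Kaplan-Meier estimation assumes that censored subjects carry the same future risk as those still followed. Censoring at this entry breaks that assumption in a known direction: medians lengthen and landmark PFS rates rise.

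The exception for earlier documented PD may often be out of reach in myeloma. Protocol 8.2.1.1 requires progression shown by one laboratory test alone to be confirmed by a repeat sample 1 to 4 weeks later. Symptomatic deterioration can be entered while that confirmation is pending.

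PFS and DOR are secondary endpoints in all three parts. Part B is open label, so the investigator records clinical progression knowing the arm. SAP 5.3.3 plans no sensitivity analysis for the primary endpoint, and the SAP describes none for PFS or DOR that would show the effect of this rule.

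**Working it through.** **Step 1: the texts side by side.** What happens to PFS or DOR when a clinical-progression entry exists:

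| Situation | Sentence under Table 8 | Table 8 rows alone |
|---|---|---|
| Documented PD before the entry | event | event |
| Documented PD after it, no new therapy, at most one missed visit | censored | event |
| Death after it, same conditions | censored as worded | event |
| PD or death after new therapy or after two or more consecutive missed visits | censored | censored |

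The second and third lines are the conflict. The definitions in Protocol 9.4.3.2 and 9.4.3.4 and SAP 5.4.5 agree with the right-hand column. The footnote explaining an adequate visit mentions missed visits and anti-cancer therapy, then trails off; it does not name clinical progression. Table 8 also has no row, and so no date, for censoring at clinical progression. By analogy it would be the last valid assessment before the entry, but two programmers could reasonably differ.

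**Step 2: an example.** Clinical progression is entered on Day 100. An M-protein sample on Day 105 meets the PD threshold, and a repeat between Day 112 and Day 133 (105 + 7 to 105 + 28) confirms it. No new therapy is started. This is documented PD by the protocol's rule, yet the sentence censors the subject because the PD was not recorded first.

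**Step 3: size.** The plan gives no median, event count or affected share for PFS or DOR, so there is no figure to reproduce. Let q be the share of events that Table 8's ordinary rows would count but this sentence removes. With exponential times, turning a share q of events into censorings at about the same time multiplies the hazard by (1 − q). A true median m then appears as m/(1 − q).

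The value m = 4 months is an assumption, prompted by the 4-month estimated treatment period in Protocol 4.4.1.3. A median of 8 months was also taken.

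- m = 4, q = 5%: 4/0.95 = 4.21 months
- m = 4, q = 10%: 4/0.90 = 4.44 months
- m = 8, q = 5%: 8/0.95 = 8.42 months
- m = 8, q = 10%: 8/0.90 = 8.89 months

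**Step 4: simulation check.** There were 3,000 runs with 40 subjects, 28-day assessments (Protocol 8.2.1) and a cut-off 6 months after the last first dose (Protocol 9). Further assumptions were 12-month accrual, PD or death within 0–1 or 0–2 months after the entry, and censoring at the last assessment before it.

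| True median | q | Median, later events counted | Median, SAP rule |
|---|---|---|---|
| 4 | 5% | 3.83–3.84 | 4.11 |
| 4 | 10% | 3.86 | 4.33–4.38 |
| 8 | 5% | 7.93–7.96 | 8.42 |
| 8 | 10% | 7.85–7.89 | 8.75–8.86 |

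The comparison is between the last two columns. For the 4-month case the inflation is about 7% at q = 5% and 12–14% at q = 10%. Six-month PFS moves from about 35% to 37% and 38% respectively. The direction was the same in every scenario run.

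**The case against.** Protocol 9.4.3.4 hands censoring detail to the SAP and points to an outside guidance table that cannot be checked here. For myeloma, Protocol Appendix 9 says clinical relapse is not used in calculating PFS. That is a sound reason not to count clinical progression as an event, and a reason to keep any analysis that does so supplementary. It is no reason to end follow-up and discard documented PD that comes later.

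The effect may also be small. The protocol calls such cases rare, and some affected subjects would be censored anyway for new therapy or missed visits. If 5% of events follow a clinical-progression entry and half of those are censored regardless, q is 2.5% and a 4-month median becomes 4/0.975 = 4.10. This stands as a limit on size; it does not remove the contradiction.

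A reader might infer four stronger points that the documents do not support:

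- **That the SAP settles that later deaths are dropped.** The sentence read alone implies it, but Table 8's death row says the reverse. It is an internal conflict to be reconciled.
- **That the myeloma schedules need 28-day visits after End of Treatment.** Protocol 8.2.1 defers to those same tables. Protocol 7.1 describes follow-up after stopping as End of Treatment assessments, the safety visit and survival status. The SAP statement "Response assessments should be performed until confirmation of disease progression, start of new anti-cancer therapy, withdrawal of consent, or death, whichever comes first" sits directly under the DLBCL visit-window table. Extra visits off drug would be new procedures.
- **That Part B's PFS hazard ratio is distorted.** No hazard ratio or hypothesis test is planned. Recording that differs by arm is possible in an open-label trial, but nothing in the documents shows it.
- **That inflation is large.** Shares of 20% and 30% gave simulated medians of about 4.8 and 5.4 months for a true 4, but shares of that size do not fit a description of rare.

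**Conclusion.** The concern holds. The sentence drops documented PD that follows a clinical-progression entry and, as worded, later deaths. It contradicts the endpoint definitions and Table 8's event rows, and it discards information that sites are asked to collect. The bias is upward for PFS and DOR. On the assumed 4-month exponential median it is about 0.2 months at q = 5% and 0.4 months at q = 10%. Both the median and q are assumptions, and the effect could be smaller. ORR and OS are not touched, and no formal test depends on PFS or DOR.

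**What to change.** Replace the sentence under Table 8 with: *Clinical progression alone is neither a PFS/DOR event nor a censoring reason; the first documented PD or death after it is an event under the ordinary Table 8 rows (the new anti-cancer therapy and missed-visit rules still apply).*

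Report the number of subjects with clinical progression by cohort or arm. Add one supplementary PFS/DOR analysis that counts clinical progression as an event.

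The cost is one SAP sentence, one count and one supplementary table, with no change to visits or data collection. Reported medians may be slightly shorter. The change should be made before database lock.

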### 5.4.4 TTR

Time to response (TTR, months) is defined as time from C1D1, or randomization, to date of first documented response (PR or better). TTR will be presented descriptively (n, mean, standard deviation (Std Dev), median, minimum, and maximum) for the subjects achieving PR or better.

#### **5.4.5 PFS**

Progression-free survival (PFS, months) is defined as the time from C1D1, or randomization, to first documented PD or death due to any cause, whichever occurs earlier (see Table 8 for censoring rules). PFS will be derived for all subjects and analyzed using similar methods as DOR.

PFS event-free rate at a landmark time T is defined as the probability that a subject has not progressed and is alive at time T. (Subjects with an intermittent event prior to the landmark will not be a part of the analysis.) PFS event-free rates at 6, 9, and 12 months (or later times if available) will be presented along with 95% CI.

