**Table 3: Phase 2 Expansion Part B**

Objectives	Endpoints
Primary	

 
Compare overall response of GEN3014 IV vs daratumumab SC in anti-CD38 mAb-naïve RRMM subjects
 
	
 
ORR
 

Secondary	

 
Compare time dependency in PK between GEN3014 IV vs daratumumab SC
 
	
 
Ctrough levels of GEN3014 IV, or daratumumab SC, on Cycle 3 Day 1
 

 
Assess the anti-tumor activity of GEN3014 IV vs daratumumab SC
 
	
 
VGPR or better
 
CR or better
 
DOR
 
TTR
 
PFS
 
OS
 
Time to next therapy (TTNT)
 

 
Assess safety of GEN3014 IV vs daratumumab SC
 
	
 
Safety: Incidence and severity of AEs and SAEs, including changes in laboratory values, vital signs, ECGs
 
Immunogenicity: Anti-GEN3014 antibodies, anti-daratumumab antibodies, anti- rHuPH20 antibody
 

Exploratory	

 
Evaluate the pharmacodynamic profiles of GEN3014 and compare with those of daratumumab
 
	
 
Pharmacodynamic markers in blood and tumor samples, including frequencies of NK cells and other leukocyte subsets, and complement analyses
 

 
Assess potential biomarkers predictive of clinical response to GEN3014 and evaluate potential surrogacy with PFS and OS
 
	
 
CCI
 
Immune cell profiling
 
DNA mutation status and gene profile (RNA-seq)
 

 
Assess MRD status
 
	
 
Rate and duration of MRD-negative remission
 

 
Explore PK/pharmacodynamic relationship (PK/anti-tumor activity) and PK/safety
 
	
 
Dose concentration response (biomarkers and/or efficacy, safety) relationship
 

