### Expansion Part A

- Anti-CD38 mAb-naïve RRMM (N=approximately 10 subjects)
- Anti CD38 mAb-refractory RRMM (N=20 subjects)
- R/R DLBCL (up to 40 subjects)
- R/R AML (N=20 subjects)

Expansion Part B will include approximately 80 anti-CD38 mAb-naïve RRMM subjects randomized to GEN3014 or daratumumab SC in a 1:1 ratio (N=40 each cohort).

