### **5.3.2      *Main Analytical Approach***

The ORR and its 95% CI, calculated by the Clopper-Pearson (exact) method, will be presented by cohort. In conjunction with the ORR, the frequency and proportion in each response category will be reported.

The ORR for subjects treated with GEN3014, as compared to the ORR in subjects treated with daratumumab SC in the Expansion Part B with anti-CD38 mAb-naïve RRMM subjects, will be presented by the response ratio and the corresponding 2-sided 95% confidence interval based on the Miettinen-Nurminen method (Newcombe, 1998). P values will not be presented. Any stratified analysis will be done using the IRT stratification factor used for randomization.

The maximum percentage change from baseline (see further details in Section 5.1.3) at any time on trial, but before the first PD, will be presented using waterfall plots.

Individual subject data listings will be provided to support response derivation.

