#### **5.4.6 OS**

Overall survival (OS, months) is defined as time from C1D1, or randomization, to death due to any cause, will be analyzed using the Kaplan-Meier method. The subjects who are alive or with no observed death will be censored at last contact date.

Median OS with associated 95% CI as well as first and third quartiles and range will be provided. Survival rates at 6, 9 and 12 months (or later times if available) will be presented along with 95% CI.

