#### **5.4.7 TTNT**

Time to next therapy (TTNT, months) for subjects in the Expansion Part B is defined as the time from randomization to the start of subsequent anti-cancer therapy. Death due to PD without start of subsequent therapy will be considered as an event. Subjects who withdrew consent to study or are lost to follow up or die due to causes other than disease progression will be censored at their last disease assessment.

TTNT will be derived for all subjects and analyzed using similar methods as DOR.

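### Part B's secondary efficacy objective sets GEN3014 IV against daratumumab SC, but PFS, OS, TTNT and VGPR or better have only by-arm summaries planned

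*SAP*

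**What the plan says.** The Part B secondary objective reads "Assess the anti-tumor activity of GEN3014 IV vs daratumumab SC" in SAP Table 3, and protocol Table 3-3 agrees. Its endpoints are VGPR or better, CR or better, DOR, TTR, PFS, OS and TTNT.

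Two Part B endpoints have an explicit between-arm estimate. The primary ORR "will be presented by the response ratio and the corresponding 2-sided 95% confidence interval based on the Miettinen-Nurminen method" (SAP 5.3.2; protocol 9.4.3.1 matches). The Cycle 3 Day 1 trough has a geometric mean ratio with a 90% CI (protocol 9.4.6.1). SAP 5.4.2 sends CR or better to the ORR method, so the ratio can be read to apply there too.

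For the four endpoints at issue, the SAP says:
- VGPR or better (5.4.1): "CBR and VGPR will be reported with its exact 95% CI, calculated by the Clopper-Pearson method", shown alongside the ORR.
- PFS (5.4.5): "PFS will be derived for all subjects and analyzed using similar methods as DOR", plus event-free rates at 6, 9 and 12 months with 95% CIs. Protocol 9.4.3.4 says "the Kaplan-Meier curves, medians, and 95% CIs of the medians will be presented".
- OS (5.4.6): "Median OS with associated 95% CI as well as first and third quartiles and range will be provided", plus survival rates at the same landmarks.
- TTNT (5.4.7): "TTNT will be derived for all subjects and analyzed using similar methods as DOR". Protocol 9.4.3.6 refers it to the OS method instead.

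The trial declares no hypotheses. SAP Section 2 and protocol 9.1 describe the Part B comparison as a first estimate of relative effect and name two measures for it, the response ratio and the trough ratio. SAP 5.3.2 rules out P values for the ORR comparison.

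**The concern.** Part B is the only randomised part of the trial. An objective that sets one drug against another is answered by an estimate of the contrast and an interval for that estimate. For PFS, OS, TTNT and VGPR or better, the plan gives each arm its own estimate and interval and stops there. Neither document mentions a hazard ratio, a Cox model, a log-rank test, a difference in landmark rates or medians, or a ratio or difference for VGPR.

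The response scale is also treated unevenly. PR or better has a ratio and CR or better can be read to have one, but VGPR or better, which lies between them, has only a single-proportion interval.

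What is at stake is whether the relative effect on these endpoints is pre-specified. If the sponsor later wants a contrast, the estimator would be chosen after the data are seen, in an open-label trial.

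**Working it through.** Part B states no alpha, power, effect size, event count or margin, so there is no figure of the plan's own to reproduce. The first check sets the stated methods side by side.

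| Part B endpoint | By-arm summary | Between-arm estimate |
|---|---|---|
| ORR | Clopper-Pearson | Miettinen-Nurminen ratio, 95% CI |
| Cycle 3 Day 1 trough | descriptive | geometric mean ratio, 90% CI |
| CR or better | as ORR | by reference to ORR |
| VGPR or better | Clopper-Pearson | none stated |
| PFS | Kaplan-Meier, median, landmark rates | none stated |
| OS | Kaplan-Meier, median, landmark rates | none stated |
| TTNT | Kaplan-Meier, median | none stated |
| DOR, TTR | responders only | none stated |

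DOR and TTR are defined only in responders, so a contrast between arms would not be a randomised comparison. They are left out of the point.

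**Precision if a hazard ratio were added.** Inputs: 1:1 allocation (SAP Section 3) and event counts that are assumed, because the documents give none. With about 80 subjects, 80 events is the ceiling. Under 1:1 allocation, SE(log HR) ≈ 2/√events, so the 95% CI is the estimate multiplied and divided by exp(1.96 × 2/√events).
- 30 events: exp(0.716) = 2.05
- 40 events: exp(0.620) = 1.86
- 60 events: exp(0.506) = 1.66
- 80 events: exp(0.438) = 1.55

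For example, an observed hazard ratio of 0.70 with 60 events has a 95% CI of 0.70/1.66 to 0.70 × 1.66, or 0.42 to 1.16.

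**Precision if a VGPR ratio were added.** Inputs: 40 per arm and assumed responder counts. The Miettinen-Nurminen limits are the values R at which (p1 − R·p2)²/V(R) = 3.84. V(R) is the variance at the proportions constrained to ratio R, with the factor N/(N−1).
- 8/40 vs 8/40: ratio 1.00 (0.42 to 2.36)
- 12/40 vs 8/40: ratio 1.50 (0.70 to 3.27)

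For the second case, the output now planned would be two separate intervals: 12/40 = 30% (16.6% to 46.5%) and 8/40 = 20% (9.1% to 35.6%).

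**Yardstick.** The ORR ratio that the plan already accepts has a 95% CI of 0.58 to 1.72 at an assumed 16/40 vs 16/40. That is a factor of about 1.7 either side of 1, similar to a hazard ratio on 60 events.

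**What a reader could still derive.** The response categories are tabulated (SAP 5.3.2), so the VGPR ratio and its interval follow from the reported counts. For PFS and OS, the arms are independent, so a landmark difference has SE = √(SE₁² + SE₂²), with each SE approximated from the reported interval. For TTNT, SAP 5.4.7 promises no landmark rates, and SAP 5.1 makes them optional in general.

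**The case against.** The strongest reply is that the scope is deliberate. SAP Section 2 and protocol 9.1 name only the response ratio and the trough ratio as the measures of the comparison. The objectives tables use the verb compare for response and PK, and assess for anti-tumor activity and safety. The safety objective also names both drugs and also gets by-arm summaries. Protocol 9.4.3.4 and 9.4.3.5 foresee that events may be too few even for Kaplan-Meier. On this view, hazard ratios on unpowered secondary endpoints are a matter of preference.

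This lowers the weight of the point without removing it. The objective still sets one drug against the other, and the ORR shows that the plan can estimate a contrast without testing anything. The small-event warning argues for a fallback, not for silence.

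For VGPR, one can argue that showing it beside the ORR implies the ratio. SAP 5.4.1 names only a Clopper-Pearson interval, while SAP 5.4.2 uses different wording for CR, so at the least a clarification is needed.

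A reader might infer more than the documents support, in two ways.
- That the randomised comparison is lost altogether. It is not: counts, curves and landmark rates allow the VGPR ratio and approximate PFS and OS differences to be worked out.
- That the arms are to be judged by whether their separate intervals overlap, with a loss of power or a distorted error rate. Neither document states such a rule, and with no hypothesis to test, power and error rate do not apply.

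**Conclusion.** The point holds as a mismatch between a comparative objective and by-arm summaries for PFS, OS, TTNT and VGPR or better. No effect estimate with its own interval is planned for any of them. It is not an error in a test, because the trial tests nothing, and part of the contrast can be derived from the planned output. It is a low-cost improvement worth making, and it does not threaten the primary result.

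The added estimates would be imprecise. The hazard-ratio 95% CI would be about the estimate multiplied and divided by 1.55 at 80 events to 2.05 at 30, and the VGPR ratio about 0.42 to 2.36 if both arms were at 20%. Event counts and response rates are assumptions. The finding that no contrast is specified rests on the text alone.

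**What to change.** For Part B, add to SAP 5.4.5 to 5.4.7, and align protocol 9.4.3.4 to 9.4.3.6:
- A descriptive hazard ratio (GEN3014 IV / daratumumab SC) with 2-sided 95% CI and no P value for PFS, OS and TTNT. Use an unstratified Cox model, or one stratified by the IRT factors where strata and event counts allow. Some of the factors are blacked out in the public text, so full stratification at 40 per arm cannot be judged from here and should not be mandatory.
- A rule, fixed in advance, that omits the hazard ratio or replaces it with a difference in landmark rates when events are too few, in line with protocol 9.4.3.4 and 9.4.3.5.

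In SAP 5.4.1, state that VGPR or better in Part B is presented with the same Miettinen-Nurminen response ratio and 95% CI as the ORR. Keep DOR and TTR descriptive by arm.

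Add a caveat to the output. The analysis set is dosed subjects by treatment actually received (SAP 4.1), and subjects may be replaced by arm without regard to the stratification factors (protocol 6.4.2.2). The estimates are therefore not a strict comparison of everyone randomised.

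If the sponsor does not want these contrasts, the alternative is to reword the objective as a description of each arm.

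The cost is a few sentences and some extra output rows, with no new data, visits or subjects. The downside is wide intervals, which should be labelled descriptive. The SAP is written to Amendment 3 while the protocol stands at Amendment 5, so the change could go into the update that realigns the two.

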## 5 STATISTICAL ANALYSES

### 5.1 General Considerations

Analyses will be carried out using SAS (Version 9.4 or higher), unless otherwise noted.

In general, continuous variables will be summarized using descriptive statistics such as mean, standard deviation (Std Dev), median, minimum, and maximum. Categorical variables will be summarized using absolute count and percentage (relative to analysis set).

Estimates of time to event variables will be provided based on Kaplan-Meier (KM) methods with the number and percentage of subjects with event or censoring reported. 95% CI of the KM estimate will be provided using the log-log transformation. Median times with 95% CI (based on the Brookmeyer and Crowley method) will be reported. Landmark event-free rates with 95% confidence intervals may also be presented.

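### SAP 5.4.5 excludes subjects with an undefined *intermittent event* before the landmark, which conflicts with its own definition of the 6-, 9- and 12-month PFS rate

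*SAP*

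**What the plan says.** SAP 5.4.5 measures PFS from C1D1 or randomization "to first documented PD or death due to any cause, whichever occurs earlier". On population and method it says: "PFS will be derived for all subjects and analyzed using similar methods as DOR". The DOR section (SAP 5.4.3, text below Table 8) gives that method: "DOR will be estimated using the KM method and the result will be displayed graphically".

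The landmark quantity follows: "PFS event-free rate at a landmark time T is defined as the probability that a subject has not progressed and is alive at time T". The next sentence, in parentheses, reads: "Subjects with an intermittent event prior to the landmark will not be a part of the analysis". The section ends: "PFS event-free rates at 6, 9, and 12 months (or later times if available) will be presented along with 95% CI".

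Four other places bear on this:

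- SAP 5.1 sets Kaplan-Meier with log-log confidence intervals for time-to-event variables. It adds, without any exclusion: "Landmark event-free rates with 95% confidence intervals may also be presented".
- SAP 5.4.6 plans OS rates at the same times, also without an exclusion: "Survival rates at 6, 9 and 12 months (or later times if available) will be presented along with 95% CI".
- Protocol 9.4.3.4 specifies Kaplan-Meier for PFS and has no landmark exclusion.
- SAP 6.1 declares no change from the protocol-planned analyses.

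**The concern.** The definition and the parenthesis cannot both be followed. The definition is a probability over all subjects. The parenthesis takes some of them out of the analysis according to what happened to them after baseline, and selecting subjects on post-baseline outcome changes what is estimated. The term that decides who is removed is not defined, so the programmer must guess.

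PFS is a secondary endpoint in Dose Escalation, Part A and Part B. At stake is whether the printed 6-, 9- and 12-month rates agree with the Kaplan-Meier curve from the same data. In Part B the rates for GEN3014 and daratumumab SC would stand side by side. Under the second reading below, the bias would differ between arms if censoring did.

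**Working it through.** **No figure to reproduce.** The documents give no planned PFS rate, median or hazard. The check compares what the rule yields with the probability the SAP defines, under the two readings that take the exclusion literally.

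**Reading A: the event is progression or death** (the PFS event of SAP 5.4.5). Removing everyone with an event by T leaves only subjects who are event-free at T, so the estimate is 100% at 6, 9 and 12 months. This needs no distributional assumption. Example with 40 subjects (the planned size of a Part B arm): if 20 have an event before 6 months and nobody is censored, the rate is 20/40 = 50%. After exclusion it is 20/20 = 100%.

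**Reading B: the event is intercurrent and of the kind Table 8 censors**, such as new anti-cancer therapy or repeated missed visits. Table 8 keeps these subjects and counts their event-free time up to censoring. Deleting them loses that time. Among those left, nobody is censored before T, so Kaplan-Meier reduces to subjects still under observation and event-free at T, divided by those subjects plus subjects with an event by T.

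Assumptions, none from the documents:

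- exponential PFS with median 4 months, so λ = ln 2 / 4 = 0.1733 per month;
- independent exponential censoring at rate μ = 0, 0.03, 0.06 or λ/2 = 0.087 per month.

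Formulas:

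- True rate: S(T) = exp(−λT)
- Rate under the rule: E / [E + λ/(λ+μ) × (1 − E)], with E = exp(−(λ+μ)T)

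Worked case, μ = 0.03, T = 6: E = exp(−0.2033 × 6) = 0.295 and λ/(λ+μ) = 0.852. The rule gives 0.295 / (0.295 + 0.852 × 0.705) = 0.330, against a true exp(−0.1733 × 6) = 0.354.

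| Censoring per month | 6 months | 9 months | 12 months |
|---|---|---|---|
| True rate | 35.4% | 21.0% | 12.5% |
| Rule, 0 | 35.4% | 21.0% | 12.5% |
| Rule, 0.03 | 33.0% | 18.3% | 10.1% |
| Rule, 0.06 | 30.6% | 15.8% | 8.0% |
| Rule, 0.087 | 28.5% | 13.8% | 6.5% |

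At 6 months the shortfall is 2.4, 4.8 and 6.9 percentage points at the three non-zero censoring rates.

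**Other medians.** A simulation of 4,000 trials with 40 subjects used medians of 3, 4, 6 and 9 months and censoring of 0, 0.03 and 0.06 per month. With censoring present, the Reading B shortfall ran from 1.3 points (median 3, 0.03 per month, 12 months: 0.049 against 0.062) to 9.9 points (median 9, 0.06 per month, 12 months: 0.298 against 0.397). Kaplan-Meier on all subjects was within 0.005 of the true value in every scenario.

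**The case against.** The strongest defence is a third reading: the parenthesis is a clumsy way of saying that subjects with an earlier event or censoring are no longer at risk at T. Kaplan-Meier works that way, and the numbers would then be right. The surrounding text gives this some support: PFS is derived for all subjects, the method is Kaplan-Meier, SAP 5.1 mentions landmark rates without an exclusion, and no departure from the protocol is declared. SAP section 1 also leaves programming notes to the Data Presentation Specification, which is not available here.

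This may be what was intended, but the sentence does not say it. Subjects who leave the risk set stay in a Kaplan-Meier analysis, as events or as censored observations. Even on this reading the sentence has to go.

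Three further points stand:

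- Reading A is an unlikely intent, since it would make every rate 100% and the planned confidence interval pointless.
- The Reading B sizes rest on assumed inputs. With 40 subjects the binomial standard error of a 35.4% rate is √(0.354 × 0.646 / 40) = 7.6 points, more than the 6.9-point shortfall at the highest censoring rate used. A bias of that size could go unnoticed, but it would not average out.
- Landmark PFS rates are descriptive. The trial tests no hypothesis, and SAP 5.1 lists such rates as optional.

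**Conclusion.** The instruction is wrong as written. Followed literally, it does not estimate the probability defined one sentence earlier: it gives 100% under Reading A, and a rate biased downward under Reading B whenever anyone is censored before T. Only the 100% result is free of assumptions. The Reading B figures depend on exponential PFS, the chosen median and independent censoring at the stated rates; none of these comes from the documents.

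A reader might infer that the SAP removes all subjects who progressed or died, so that landmark PFS is certain to be wrong in every cohort. The documents do not support that. The text says *intermittent event*, which is undefined and is not the PFS event of the same section. Under Reading B a cohort with no such censoring before T has no bias.

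A reader might also infer that the Part B comparison is compromised. That too goes beyond the text: no PFS test or hazard ratio is planned, and ORR, sample size, PFS medians and Kaplan-Meier curves are untouched. This is a clear error in a descriptive output. It should be corrected, but the trial's main conclusions do not depend on it.

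**What to change.** Delete the parenthesis in SAP 5.4.5. State that the 6-, 9- and 12-month PFS rates (and later ones) are read from the Kaplan-Meier estimate on all FAS subjects under Table 8 censoring, with the log-log 95% confidence interval of SAP 5.1. Before deleting, ask the author what was meant. If it was a specific intercurrent event, name it and handle it as censoring in Table 8, not by exclusion. Check that the Data Presentation Specification does not repeat the exclusion.

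The cost is one or two sentences in the SAP. No data collection, sample size or other analysis changes.
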